#### 4.8 Interim Analysis

We are only collecting 8-10 participants as a proof-of-concept study for pilot data to support grant applications for larger clinical trials. Therefore, an interim analysis is not necessary.

### 5 STUDY INTERVENTION (DEVICE, DRUG, OR OTHER INTERVENTION)

Detailed procedures can be found in "Appendix A. Extended Intervention Document." Following monitor initialization and registration, participants will complete a 14-day "run-in" period during which they will wear the Fitbit (=10 days of compliance) but no physical activity promotion will occur. This establishes participant compliance, understanding of the Fitbit, and baseline daily step data to generate the first individualized step goals for the physical activity promotion period. Individuals who do not meet compliance requirements needed to set the daily goals (>10 days with at least 1,000 steps). Participants who are compliant will be exposed to physical activity promotion for 8 weeks. During this period of time, participants will receive an SMS message (or email if they don't have a smart phone) each morning containing a personalized step count goal for the day and a link which they will click to confirm receipt of the goal. To set the daily goal, the preceding 10 days of step data will be rank ordered and 60th percentile step count will be set as the goal for the following day. Calculation of daily goals will be automated, and will occur prior to our standard goal communication time (8 am).

### 6 STUDY INTERVENTION ADMINISTRATION (IF APPLICABLE)

N/A

### 7. SAFETY MANAGEMENT

Definitions:

- *Adverse Event (AE)* - An adverse event is any unfavorable and unintended diagnosis, sign (including an abnormal laboratory finding), symptom, or disease temporarily associated with the study intervention, which may or may not be related to the intervention. AEs include any new events not present during the pre-intervention period or events that were present during the pre-intervention period, which increased in severity.
- *Serious Adverse Event (SAE)* – A serious adverse event is any untoward medical occurrence that results in death, is life-threatening, requires or prolongs hospitalization, causes persistent or significant disability/incapacity, results in congenital anomalies/birth defects, or, in the opinion of the investigators, represents other significant hazards or potentially serious harm to research

participants or others.

- *Unanticipated Problems* – Unanticipated problems are not included in the 45 CFR part 46, but are defined by the OHRP as any incident, experience or outcome that meets all of the following requirements: 1) unexpected events that are 2) related or possibly related to participation in the research that 3) place subjects or others at greater risk of harm than was previously known or recognized. All three criteria above must be met to qualify the event as an unanticipated problem.

Monitoring Roles:

- *Medical Monitor* - A physician or other designated medical practitioner who is responsible for the day-to-day safety aspects of the study and can be consulted regarding individual participants.
- *IRB* - A committee established by the grantee/sponsoring Institution to review and approve research involving human subjects. The IRB ensures human subject research is conducted in accordance with all federal, institutional, and ethical guidelines.

The research described in this proposal meets the definition of human subject's research of a biomedical or behavioral nature. As such, we have approval from human subjects research from the IRB for Biomedical Research at UNC-CH. This approval has been obtained prior to the recruitment or enrollment of study participants and the collection of any study-related data. The MSU study team and IRB for Biomedical Research will rely on the UNC-CH IRB for Biomedical Research as the single IRB for the duration of the proposed study. The proposal is considered a low-risk study and an early phase clinical trial. As such, a formal Data Safety Monitoring Board may not be required. However, the final determination of the need for a Data Safety Monitoring Board will be made in collaboration with NC TraCS.

[name] and [name] will oversee data collection monitoring and all issues related to participant safety, data collection protocols, and participant confidentiality. [name] and [name] will collect all adverse events for any study-related issues pertaining to safety and all adverse events will be reported to [name] from the MOTION Science Institute at the UNC-CH. [name], Co-Director of the MOTION Science Institute, will be responsible for the independent safety monitoring since he is not a co-investigator or collaborator on this project. [name] has previous experience as a PI in clinical trials for patients with knee injuries (NCT02605876) and therefore has the experience and knowledge regarding the scientific area of study and study design, which will be important in understanding the analysis and interpretation of the data to ensure participant safety as well as ethical, scientifically rigorous study conduct.

It is not anticipated that there will be any significant physical or psychological risks associated with this study. However, federal regulations require prompt reporting to the IRB at UNC-CH, all injuries, adverse events, or other unanticipated problems involving risks to patients or others that occur during a patient's participation in this research study. Study team members who become aware of any adverse event or unanticipated problems related to the study will notify [name] or [name], immediately. Study team members will have contact information for both PIs for daytime, evening, and weekend hours. If both [name] and [name] are not available for contact when a study team member becomes

aware of a study-related adverse event, [name], the Medical Monitor on the study, will be contacted. Once [name] or the PI at MSU are contacted about the event, [name] will make appropriate reports in accordance with the UNC-CH IRB guidelines. This will include notification of the UNC-CH IRB and the Safety Officer.

[name] or [name] will report all adverse events (both serious and non-serious), unanticipated problems, study progress, and protocol deviations to the safety officer, [name] (who is not affiliated with the study), on a biannual basis (every 6 months) or as requested in a detail and summary format. All adverse events (both non-serious and serious) will be collected, analyzed, and monitored in the study's adverse event log, which is kept in [name] and [name] regulatory files on a secured server. [name] will also ensure the enrollment rate is consistent with the project timeline, verify that the participants meet enrollment criteria, and that each subject has been consented.

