#### - Potential Risks:

- Risk of pain or injury from MRI
  - How to Minimize Risk: Participants will be screened at time of consent and the day before each MRI as per the protocol of the Biomedical Imaging Research Center to exclude those with cochlear implant, metal in body (i.e., non-surgical), claustrophobia, history of seizures, pacemaker, liver disease, high blood pressure, or diabetes from receiving an MRI. Participants will also wear ear plugs and offered MRI-safe headphones to protect their ears from loud noises. Both scanners are Food and Drug Administration (FDA)-approved and all new sequences will contain the same safeguards as standard (FDA-approved) clinical sequences to prevent harm to participants.
- Risk that someone outside of approved research personnel could know participant information (breach of confidentiality).
  - How to Minimize Risk: The following actions will be taken to protect a participant's private information: 1) Study personnel will have access to private consenting and research collection areas or participant interactions. 2) Data will only be inputted and reviewed by Institutional Review Board (IRB)-approved study personnel. 3) Paper records will be stored in locked filing cabinets and electronic files will be stored on REDCap and password-restricted, secure cloud-based storage maintained by a dedicated IT staff member in the Department of Exercise and Sport Science that can only be accessed by IRB-approved study personnel.

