### **3.9 Screen failure procedures:**

A participant will screen out from the study if:

- 1) They don't meet screening criteria (<8000 steps per day over 7 days during the initial actigraph physical activity monitoring period)
- 2) They are non-compliant with the Fitbit monitoring "run in" observation period over 14 days. A participant will be determined non-compliant if they fail to accumulate 1,000 daily steps for more than 5 days during this period of time.

Participants will be notified that they failed the screening to qualify for the intervention, return the actigraph or fitbit monitor, and not continue with the baseline visit, intervention, or follow-up visit.

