#### ***Description of Instructions for Administering the Physical Activity Promotion Exposure***

Following the screening, automated, scheduled percentile-based goals will be delivered to the participant every morning via a personalized text message. The goal setting feature functions via automated processing of daily participant-level steps per day data which is used to develop a daily steps goal. Visual representation of the daily goal setting text message can be seen in Figure 1.

After screening, participants will be made aware of that the physical activity promotion period has started and a study team member will describe the specifics of the Daily Step Promotion intervention. This will include the following descriptions and instructions:

1. The participant will receive a daily text message in the morning which will include their daily step goal and a link that they will need to click to confirm receipt of the text message.
2. The link will provide access to a personalized dashboard that will display their step counts during the study period and number of days during which they achieved their step goals.
3. If they do not click the link, they will be reminded to do so later in the day via follow-up text message.
4. If they do not click the link for 2 consecutive days, they will be contacted by a study team member via phone.
5. The PA data collected by the Fitbit Charge 2 monitor will update throughout the day without any additional required effort.
6. The PA goal will change daily.
7. The participant should attempt to meet or exceed their daily PA goal.

Following this communication, the participant will complete the 8-week intervention period with minimal contact from the study team with exception of a weekly “check-in” phone call or text message, participant non-compliance, or technical difficulty. During week 6 of the study period, participants will be contacted by a study team member to schedule an appointment to complete the 8-week study visit and they will receive a reminder via text 1 week prior to the date of the visit. At the time of the 8-week study visit, a study team member will provide instructions regarding de-registration of the Fitbit Charge 2 monitor from the study account in order to re-purpose the device for personal use. The study team member will also confirm the appropriate method for delivery of study renumeration.

**Figure 1.** Example of text messages received by participants.

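### The AE definition is anchored to the step intervention, so a non-serious baseline-MRI injury that does not worsen, and new events before promotion starts, are not clearly AEs for the log

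*Combined protocol and SAP*

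**What the plan says.** Section 7 (Safety Management, Definitions) has a two-sentence AE definition. The first sentence covers an unfavourable diagnosis, sign, symptom or "disease temporarily associated with the study intervention, which may or may not be related to the intervention". The second continues: "AEs include any new events not present during the pre-intervention period" "or events that were present during the pre-intervention period, which increased in severity". Neither sentence mentions consent or study procedures, and neither gives an end date.

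Other text in section 7 is wider. The definition of a serious adverse event (SAE) is tied neither to the intervention nor to a period: "A serious adverse event is any untoward medical occurrence that results in death, is life-threatening, requires or prolongs hospitalization", and so on. An unanticipated problem is tied to taking part in the research, but must also be unexpected and show a greater risk than was known. The IRB is to be told promptly of all injuries, adverse events and other unanticipated problems "that occur during a patient's participation in this research study". The study log holds adverse events. The six-monthly report to the safety officer covers adverse events, unanticipated problems, progress and protocol deviations.

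Section 1.3 lists two risks, "Risk of pain or injury from MRI" and breach of confidentiality. Section 3.2 puts the first MRI at the baseline visit. Sections 3.3 and 5 then describe a 14-day run-in without promotion, followed by 8 weeks of promotion. Section 3.4 puts the second MRI and a further Actigraph week after that.

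**The concern.** The reference state for an AE is the period before the intervention, and the first exposure to the one named physical risk falls inside that period. A minor injury at the baseline scan then becomes part of the background against which later events are judged.

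People who fail the run-in are the clearest case. They have already been scanned, yet section 3.9 treats them as screen failures who will "not continue with the baseline visit, intervention, or follow-up visit". They never start the intervention, so it is hard to see how a non-serious event of theirs meets the definition.

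Active questioning has a similar limit. Appendix A says that "the participant will complete the 8-week intervention period with minimal contact from the study team with exception of a weekly" check-in and a few other contacts. The section on adherence and compliance monitoring uses that weekly contact to ask about knee injury and other complications. No such question is specified after the baseline scan or at the end of the run-in.

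At stake is the completeness of the AE log and of the summaries that the safety officer receives. Because section 1 presents this pilot as the step towards larger randomised trials, a summary that leaves out baseline-scan injuries would look somewhat too favourable.

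**Working it through.** **1. The plan's timeline.** The Synopsis gives screening 1 week, baseline monitoring (run-in) 2 weeks, intervention 8 weeks and follow-up monitoring 1 week. The sum is 1 + 2 + 8 + 1 = 12 weeks, which matches the 12 weeks in section 2.3.

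**2. Each period and scan against the two sentences of the definition.**

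| Period or procedure | First sentence: associated in time with the intervention | Second sentence: new since, or worse than, pre-intervention | Reading |
|---|---|---|---|
| Screening (1 week) | No | Only if it later worsens | Outside |
| Baseline MRI | No; it precedes the run-in and promotion | Only if it later worsens | Outside |
| Run-in (2 weeks) | No, unless the run-in is part of the intervention | Only if it later worsens | Outside, or arguable |
| Intervention (8 weeks) | Yes | Yes | Inside |
| Follow-up MRI and last week | Unclear; no end date is given | Yes; it is new since the pre-intervention period | Not clearly excluded |

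I read the word temporarily in the first sentence as temporally. No causal link is required.

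**3. Size in weeks.**
- Screening plus run-in: 1 + 2 = 3 weeks; 3/12 = 25%.
- If the run-in counts as intervention, because section 5 describes it under that heading: 1 week; 1/12 = 8%.
- Appendix A gives the run-in as 10 days, not the 14 of sections 1.2, 3.3 and 5. With 10 days, the pre-intervention time is 1 + 10/7 = 2.4 weeks of 1 + 10/7 + 8 + 1 = 11.4.

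**4. Size in scans.** One of two scans per participant is clearly outside. With the 10 enrolled in section 4.7, that is 10 × 1 = 10 scans. With the maximum of 12 in Appendix A (Monitoring Manual) it would be 12 × 1 = 12.

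**5. Do the other routes pick up a non-serious baseline-scan injury?**
- SAE: no, the event is not serious.
- Unanticipated problem: not normally. Section 1.3 already names the risk, so an ordinary case is neither unexpected nor evidence of a greater risk than was known.
- IRB rule: yes, since it covers all injuries during participation. But the instruction for staff to notify the PIs is triggered by adverse events or unanticipated problems; injuries are not listed in it.
- Collection of AEs for any study-related safety issue: this uses the defined term, so it inherits the limit.
- Log and safety-officer report: no defined entry, because the event is neither an AE nor an unanticipated problem.

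Such an injury is therefore reportable to the IRB but has no defined route into the log.

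**The case against.** The best defence is that the definition is looser than it may appear. It says that AEs include certain events, not that they are limited to them. It does not require relatedness. It also counts pre-existing events that worsen, so a baseline-scan injury that became worse during the 8 weeks would be logged. All this is correct and narrows the point to new, non-serious, non-worsening events before promotion. It does not remove it: the first sentence must still be met, and a scan two weeks before promotion starts is not naturally associated in time with it.

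A reader might go further and infer that both scans are outside, making 20 sessions with 10 enrolled; that 4 of 12 weeks are outside; or that the log must show zero MRI injuries. The documents do not support this. The follow-up scan and the last week come after the intervention, and an injury then is new relative to the pre-intervention period, which the second sentence includes. The first sentence leaves that period open to dispute, so two people could log the same event differently, but that is ambiguity, not exclusion.

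Two further objections have some force. Section 3.9 does not say that safety events in run-in failures are dropped; the loss follows from the definition, and the IRB rule still covers these people. And sections 4.4 and 4.5 list no safety endpoint, while section 4.6 says the pilot's output is effect sizes for grant proposals, so the effect on the later trial is indirect.

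**Conclusion.** The point holds in a limited form. As written, a non-serious injury at the baseline MRI that does not worsen, and a new non-serious event in screening or run-in, are not AEs for the log or for the AE part of the safety-officer summaries. This includes events in people who fail the run-in after being scanned. The extent is 1 of 2 scans per participant (about 10 in all) and 3 of 12 weeks, or 1 of 12 if the run-in is intervention.

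This rests on three assumptions: the study intervention means step promotion; the pre-intervention period runs up to the start of promotion; and all 10 enrolled are scanned at baseline. The documents give no rate of MRI injury, so the number of missed events cannot be estimated. Section 7 expects no significant risk, so it may well be small.

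The AE definition and the IRB reporting sentence in the same section have different scopes and must be reconciled. This is a correction to make for complete safety recording; it does not affect the efficacy analysis.

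**What to change.** In section 7:
- Define an AE as any untoward event from written consent to the end of the post-intervention Actigraph week, associated in time with the intervention or with any study procedure, including both MRIs, whether or not related.
- Record the onset period: screening, run-in, intervention or post-test.
- State that people who fail the run-in stay in the AE log, and correct section 3.9, since they have already had the baseline visit.
- Ask the existing injury question after the baseline scan and at the end of the run-in. Ask it at the return of the last Actigraph only if a contact already takes place then; section 3.4 describes fitting that monitor but not its return.
- Reconcile the run-in length (14 or 10 days), because it sets the boundary between onset periods.

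The cost is one rewritten definition, a log field and two extra askings, with a third only if a contact exists. The first falls at the baseline visit. The second falls when participants are told that promotion has started (Appendix A) or that they have failed screening (section 3.9). No new visit is needed. The downside is that the reported AE count may rise slightly.

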## 8. DATA COLLECTION AND MANAGEMENT

All data storing and sharing methods will be approved by the UNC-CH's Institutional Review Board.

In Person Study Data Protections: Prior to performing any study related activities, potential adult participants will provide written informed consent. All consent procedures will be completed by qualified and trained members of the study team. This includes informing each potential participant of the purpose of the project, possible risks, their personal rights, and potential benefits of the study. All possible exclusion criteria will be verified following informed consent. Extreme care will be taken to ensure that there will be no breach of participant confidentiality.

Outcomes Data: All outcomes data will be managed using REDCap, which is a secure online platform for building and managing online databases provided at no cost to investigators at UNC-CH. The study team has been using REDCap for the past 5 years and is versed in building, acquiring and securing data using this database. REDCap also provides automated export to statistical packages (e.g. R, SPSS, and SAS) that will be used to analyze data from this study. UNC-CH also offers REDCap training twice a month as well as onsite support for assistance in building or managing REDCap databases. All pre-processed and post-processed Actigraph physical activity data, magnetic resonance imaging data, patient-reported outcome data will be stored electronically on a secure password-protected server maintained by UNC-CH. Only investigators with IRB and PI clearance will be given access to the password-protected folders on the secure server. All individuals must have current UNC-CH online access credentials to access the server and personal access will be reviewed annually to purge or renew personnel access. The PI can remove access to the server for individuals if necessary.

- Data Entry: data will be entered into REDCap from electronic files by investigators (i.e. processed magnetic resonance imaging data and joint tissue metabolism) or directly by study participants (i.e. demographics, patient-reported outcomes). Outcome measures will be cut and pasted from electronic files or collection software into REDCap to minimize data entry error. All outcome measure data will be entered by two individual investigators.
- Data Editing: means and standard deviations for datasets will be calculated each month and crossed referenced between databases for each investigator. If means are different investigators will look to determine which outcomes differ. In the case that investigators cannot come to a consensus on the correct outcome measure, the PI will act as an arbiter.

- Updating: data may need to be updated due to an error in data entry. After the incorrect data point has been determined the PI should be notified and the Signature Log should be signed indicating who changed data in the spread sheet, what data was changed, for what reason was it changed as well as the time and date it was changed. A new database with the current date should be created. The previous database with the error will not be deleted.
- Statistical Analyses: data will be reported directly from REDCap to statistical analysis software for statistical analysis.

Fitbit Data: Each participant will be assigned a unique participant identifier (PID) code generated and stored in the Microsoft Structured Query Language (SQL) database following the informed consent process. This PID code will be used to label participant data so that the data remain de-identified. Only investigators with IRB and PI clearance will be given access to the password-protected folders on the secure server which will be administered by a Co-Investigator.

Fitbit Data Protections: We will be storing participant demographics, mobile device information, and Fitbit Versa 2 PA monitor-related data using Microsoft SQL Server database software. Data for each participant will be de-identified and stored with a unique study identifier to maintain confidentiality. We will utilize a normalized schema design which will facilitate indexing (for performance), strong data types (for stability and data integrity), and User-Level security to allow us to maintain access control lists for accessing data, reading data, writing data. Data backups will be done utilizing the software's built-in backup scheduling mechanism. This will create daily, full, backup files that will reside in a designated storage location and access will be governed by an access control list which will allow us to maintain a need-to-know policy within the study team. This approach, using Microsoft SQL Server, will also allow us to take advantage of industry best-practice and facilitate the scaling of these practices in the future development of larger-scale clinical trials. For redundancy, we will backup files to separate external solid-state password protected hard drives on a weekly basis at both research sites.

